### Data collection process

Please see the section titled “Outcome/endpoint and other variable definitions, and instruments used” for a full description of this process.

## **Screening and Enrollment**

### Screening

Because CCRC research interns provide 24/7 ED coverage, and ED pharmacy is also covered 24/7, there is no restriction as to the time of day or day of week when enrollments can take place. However, to enhance investigator oversight, patients will only be enrolled when specific ED Pharmacists are on shift, who are the primary investigators. This includes [name], [name], and [name]. If those pharmacists are not at the site, the patient will not be enrolled.

ED pharmacists received an Epic alert any time a patient meeting DKA criteria is admitted to the ED. The pharmacist will alert the CCRC research intern to confirm inclusion/exclusion and approach the patient for study participation. CCRC interns will also watch the ED track board for patients admitted with a chief complaint of DKA, nausea, vomiting, abdominal pain, hyperglycemia, or similar. Alternatively, an ED pharmacist or attending physician will notify Research of a potential patient by calling the 24/7 intern bat phone.

Labs: in order to confirm inclusion/exclusion criteria, the patient will need to have had the following labs completed (*which are standard of care for any patient with DKA on the differential diagnosis. These are not extra labs that the study investigators want, rather, they will already be collected by any provider for any patient with presumed DKA*):

- Arterial or venous pH  $\leq 7.3$
- Serum Bicarbonate  $\leq 18$  mEq/L
- Presence of ketonuria or ketonemia (beta-hydroxybutyrate  $> 0.27$  mmol/L)
- Anion Gap  $> 10$
- Blood sugar  $> 250$  mg/dL

All patients who present with symptoms of possible DKA should receive these labs under standard of care, per Regions Hospital DKA Protocol. Should any of these labs be missing, the patient will not be eligible for the study.

The research intern will confirm inclusion and exclusion criteria using a RedCap screening checklist, and obtain permission from the patient’s attending to approach for study consent.

### Consent

If fully eligible, research staff will approach the patient for consent, either by calling the patient’s room phone, mobile phone, or entering the patient’s room in appropriate PPE. (Please see the “Setting/Environment/Organizational

feasibility” section for COVID-19 safety information.) Since DKA can sometimes cause confusion, if a patient is deemed by the care team to be incapable of informed consent, a patient’s legally authorized representative may be approached instead. The patient or LAR may sign the consent form either on paper or electronically in RedCap.

### Randomization

An Excel file with rows numbered 1 through 150 will be populated with a randomization column. Using Excel randomization functions, a research staff member who will not be involved in consenting will assign either the number 1 (control) or 2 (intervention) to each row number, ensuring 75 of each are populated. We chose the number 150 based on the expected sample size of 132, plus extras in case of higher-than-expected enrollment. The research staff member will then black out (black highlight over black font) the randomization column, so other team members are blinded to future assignments. Upon consent of an eligible patient, research staff will enter subject information in the next available row, and randomization status will be unblinded by removing the black highlight for that row only.

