### Enrollment

Once the patient is randomized, the CCRC intern will notify the ED pharmacist who will determine if patient is currently taking basal insulin and, if they are taking basal insulin prior to admission, will verify the home basal dosing. CCRC research staff will be notified of the dosing order from the randomization and will place the appropriate order. The patient will either receive 0.2 u/kg insulin glargine, current (prior to admission) basal insulin dose, or no additional treatment study protocol. CCRC staff will abstract the study data points from the patient’s EMR while the patient is in the Emergency Department, throughout their hospital stay, and again at the time of discharge. The ED pharmacist will time the insulin glargine dose to be administered optimally within two hours after initiation of the IV insulin infusion.

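### The allocation list is hidden only by reversible cell formatting, with no restricted access, role separation or stamped release log described, so concealment of the next assignment is not secured

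*Combined protocol and SAP*

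**What the plan says.** In the Randomization section of the combined protocol and SAP, a staff member with no part in consenting fills 150 Excel rows with arm codes, 75 per arm. Concealment takes one step: "The research staff member will then black out (black highlight over black font) the randomization column". Its stated purpose is "so other team members are blinded to future assignments". Once an eligible patient has consented, "research staff will enter subject information in the next available row". The section then explains how the arm for that patient comes to light: "randomization status will be unblinded by removing the black highlight for that row only".

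On roles, the Consent section says that "research staff will approach the patient for consent". Screening says: "The pharmacist will alert the CCRC research intern to confirm inclusion/exclusion and approach the patient for study participation". Enrollment continues: "Once the patient is randomized, the CCRC intern will notify the ED pharmacist".

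Strengths and limitations adds the assurance that those enrolling will not know the upcoming arm. The ground it gives is that someone outside the consent process prepares the scheme. Data Confidentiality and Privacy limits access to the REDCap database to the study team; it does not mention the Excel file.

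**The concern.** Black text on a black fill leaves the value in the cell. Selecting the cell or changing its format shows it. A user of the file is kept from the rows below only by the instruction to uncover one row at a time.

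The trial describes no placebo and the arm is known once assigned, so concealment before enrollment is the main protection against selective enrollment. If the person deciding whether to approach a patient knew the next arm, patients with a long or short expected stay could be steered toward or away from it. The arms would then differ before any treatment, on a characteristic tied to the primary outcome of ICU length of stay.

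**Working it through.** **1. Mechanism against claim.** The claim in Randomization and in Strengths and limitations is that future assignments are unknown to the team and to enrollers. The mechanism is cell formatting, plus a list-maker who does not seek consent. The second part settles who generates the list, not who can read it afterwards. No section describes a password, locked sheet, custodian, envelopes or central release.

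**2. Who uses the file.** The term research staff covers the list-maker, those who seek consent and those who enter the row. The intern role approaches the patient and later reports the randomization to the pharmacist. No section separates the file's user from the enroller, and the uncovering of a row is written in the passive, without naming who does it.

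**3. Room for discretion before randomization.** Two steps lie at least partly with research staff: whether to approach a patient, and confirming the inclusion criterion that glargine can feasibly be given within 2 hours of the infusion start. Other steps lie outside their control. Five laboratory criteria must be met, the attending must permit the approach, and a representative may be asked instead only where the patient is "deemed by the care team to be incapable of informed consent".

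**4. The plan's own figure, used as a yardstick.** Sample size gives 66 per arm, coefficient of variation 0.6, alpha 0.05, power 80% and a detectable ratio of about 1.31.
- SD on the log scale = sqrt(ln(1 + 0.6²)) = 0.5545.
- Ratio = exp((1.960 + 0.842) × 0.5545 × sqrt(2/66)) = 1.31, which reproduces the plan.
- Yardstick: ln 1.31 = 0.2700.

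The concern does not depend on this figure. Sample size refers to length of stay without identifying it as ICU stay.

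**5. How predictable the next arm is.** Over 20,000 random orderings of a 75/75 list, an enroller who knows all past assignments guesses the next correctly about 53% of the time across 132 patients. With the column readable, the figure is 100%.

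**6. Illustration of size (all steering inputs assumed).** There is no true effect, and k of the 66 slots in one arm go only to patients whose predicted stay is above the median. Predicted and actual log stay correlate at rho.

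Log shift = (k/66) × rho × 0.5545 × 0.798, where 0.798 = sqrt(2/π) is the mean of a standard normal above its median. For k = 10 and rho = 0.3: (10/66) × 0.3 × 0.5545 × 0.798 = 0.0201, and 0.0201/0.2700 = 7.4%.

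| rho | k | Log shift | Share of 0.2700 | Wilcoxon false positives |
|---|---|---|---|---|
| – | 0 | 0 | 0 | 4.9% |
| 0.3 | 2 | 0.0040 | 1.5% | 4.9% |
| 0.3 | 5 | 0.0101 | 3.7% | 4.9% |
| 0.3 | 10 | 0.0201 | 7.4% | 5.3% |
| 0.5 | 10 | 0.0335 | 12.4% | 6.2% |

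The false-positive column comes from 40,000 simulated trials with lognormal stay, 66 per arm and a two-sided test at 0.05; the Monte Carlo standard error is about 0.11 points. A repeat gave 5.1% with no steering, and 5.2% and 6.1% for the last two rows.

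**The case against.** The plan is not without protection, and the case for it is a fair one.

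- The list-maker is kept out of consenting, and a row is uncovered only after consent.
- Each entry goes into the next row, so a sequential record of patient against arm does exist. It would be wrong to say that there is no log; what is not described is a time and user stamp.
- Eligibility is confirmed on a REDCap checklist.
- Under Screening, an ED pharmacist is alerted to each patient who meets DKA criteria, and enrollment happens only while specified pharmacist investigators are on shift. An intern who passed over a patient would do so where an investigator knew of that patient.
- The 2-hour feasibility judgment is not shown to be the intern's alone, since the pharmacist times the dose.
- Strengths and limitations is a summary and need not restate the mechanism.

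All of this stands, and it weakens the route from a readable list to a biased comparison. None of it stops a person with the file open from reading later rows.

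A reader might infer that enrollers do open the file and see the next arm. The documents do not establish that. They leave unstated who opens it, which is a gap in roles and access and not evidence of exposure.

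**Conclusion.** The point holds as one about an unsecured procedure. The stated concealment is reversible formatting in a working file, and access, role separation and stamped release are not described. Confidence in that is high, because it rests on the text alone. Confidence that bias would follow is low: nothing shows that anyone would look ahead, and the size of any bias cannot be derived from the documents. Under assumed modest prediction of stay it is small (a shift of 1.5% to 7.4% of the detectable log ratio, with false positives of 4.9% to 5.3%).

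A reader might infer a badly inflated error rate. The same simulation does give 10.8% for 10 steered slots in one arm, and 31.1% for 10 in each arm steered in opposite directions (20 of 132 patients). Both figures need perfect prediction of stay, which nothing in the documents supports, so they should not be cited as the expected consequence.

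The change is still worth making, because the assurance matters in a trial with no placebo described and is cheap to secure. If an unwritten access restriction is already in place, stating it would resolve the access part of the point.

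**What to change.** Have the uninvolved staff member hold the list where enrollers cannot view it: in the REDCap randomization module if the site has it, otherwise in sequentially numbered opaque sealed envelopes. Release one assignment only after eligibility and consent are recorded, and log each release with time and user. Amend Randomization and Strengths and limitations to describe the mechanism used.

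Both options work on any shift when the specified pharmacists are present, without the list-holder on site. REDCap already serves screening, consent and data entry, but the documents do not say whether its randomization module is available, hence the fallback.

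The cost is a small set-up effort and two amended paragraphs. Sample size, power and alpha are unchanged, and no patients, laboratory tests or visits are added.

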### Enrollment

Once the patient is randomized, the CCRC intern will notify the ED pharmacist who will determine if patient is currently taking basal insulin and, if they are taking basal insulin prior to admission, will verify the home basal dosing. CCRC research staff will be notified of the dosing order from the randomization and will place the appropriate order. The patient will either receive 0.2 u/kg insulin glargine, current (prior to admission) basal insulin dose, or no additional treatment study protocol. CCRC staff will abstract the study data points from the patient’s EMR while the patient is in the Emergency Department, throughout their hospital stay, and again at the time of discharge. The ED pharmacist will time the insulin glargine dose to be administered optimally within two hours after initiation of the IV insulin infusion.

### **Interventions and Treatments**

#### Intervention group-specific

For patients who are randomized to the intervention group, subcutaneous insulin will be ordered as follows:

Prior to administration basal insulin (generic)	Prior to administration basal insulin (brand)	Dose equivalent of insulin glargine
Insulin glargine	Lantus; Basaglar, Semglee	1:1
Insulin degludec	Tresiba	1:1
Insulin detemir	Levemir	1:1
None	None	0.2 units/kg

If the patient is in the intervention group, the ED pharmacist and/or research intern will determine if the patient was taking basal insulin prior to admission. If the patient was not taking basal insulin prior to admission, the patient will receive 0.2 units/kg insulin glargine. If the patient was taking basal insulin prior to admission, the patient will receive their home insulin glargine dose.

Once the appropriate dose is determined, the research team will order the randomization dose of study medication and the ED pharmacist will time the study medication to begin within 2 hours after initiation of the IV insulin infusion. The dose will come from IV pharmacy and dispensed in a 1 mL insulin syringe. These syringes are then tubed to the ED. CCRC interns may facilitate this process by picking up the dose from the ED pharmacy or watching the tube stations closely for the dose to arrive, as nurses are sometimes too busy to check these stations on a regular basis. Once the insulin is provided, the nurse will administer the dose. Since the dose if not on basal insulin at baseline is weight-based, a current weight will be taken if not already done at admission. Research staff will ask the RN to complete this.

Research interns will complete follow-up evaluation of incidence of hypoglycemia or hyperglycemia after IV insulin infusion discontinuation. This step will be done in conjunction with one of the study investigators.

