Time of first anion gap < 12	Calculate time to resolution	Continuous
Presenting serum bicarbonate level in mEq/L	Inclusion/exclusion criteria	Continuous
Time of first serum bicarbonate < 15 mEq/L	Calculate time to resolution	Continuous
Presence of ketonuria or ketonemia on presentation	Inclusion/exclusion criteria	Binary
Presenting Beta-Hydroxybutyrate in mmol/L	Inclusion/exclusion criteria	Continuous

Type I or Type II Diabetes	Descriptive	Binary
Prior to admission history of current basal insulin usage	Treatment determination if in intervention arm	Binary
Home Insulin Dose	Treatment determination if in intervention arm	Continuous
Time of IV insulin infusion initiation	Ensure protocol compliance Start of outcome measure	Date/Time
Time of IV insulin infusion discontinuation	Outcome	Date/Time
Time of SC insulin glargine administration	Descriptive Ensure protocol compliance	Date/Time
Exact dose of SC insulin glargine administered	Descriptive Ensure protocol compliance	Date/Time
Weight in kg	Determine insulin glargine dose for study order	Continuous
Date/time of ICU admission	Calculate ICU LOS post-infusion for study outcome	Date/time
Date/time of ICU discharge (defined as time of service switch to progressive care or general medicine)	Calculate ICU LOS post-infusion for outcome	Date/time
Date/time of IV insulin infusion start	Calculate LOS post-infusion for study outcome	Date/time
Date/time of hospital discharge	Calculate LOS for study outcome	Date/time

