### Statistical analysis plan

The primary outcome and secondary outcomes 1-4 and 7 will follow the same analysis plan to study the difference in the distribution of time to an endpoint. First, the distributions for each of these outcomes will be evaluated to determine if the distribution is normal or non-parametric. If the distribution is normal, that outcome will be analyzed using a two-tailed unpaired t-test. If the distribution is non-parametric, that outcome will be analyzed using a Wilcoxon rank sum test. We expect length of stay data to follow a non-parametric distribution. In secondary outcome 2, the outcome measured is the time at which all of the necessary criteria are hit for the first time simultaneously, which accounts for the transient nature of some of these measures.

Secondary outcomes 5-6 will measure the prevalence of each of these outcomes. Prevalence was chosen over incidence in order to account for multiple instances of rebound hyperglycemia or hypoglycemia occurring within the specified timeframe for each and also the amount of time it takes to clinically reverse these conditions. For both of these outcomes, a two-proportion z test will be run to find the difference in the amount of time each treatment arm cumulatively spent with the specified condition. Finally, for the outcomes relying on certain lab values, we will examine time from IV insulin infusion start to outcome labs in both groups. If there is significant variability between the experimental and SOC arms, we will adjust for this statistically. Group randomization should ensure that variability is

equally distributed between groups, however, there is a chance of bias (e.g., if the experimental group fares better and thus are slower to get nursing checks.)

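### Prior basal insulin use selects the intervention regimen, but it is ascertained after allocation, tied mainly to one arm, and absent from the primary analysis

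*Combined protocol and SAP*

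**What the plan says.** The intervention section sets two regimens: "If the patient was not taking basal insulin prior to admission, the patient will receive 0.2 units/kg insulin glargine", and "If the patient was taking basal insulin prior to admission, the patient will receive their home insulin glargine dose". Controls get no study dose.

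Three places describe how the deciding factor is obtained, and they differ:

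- **Enrollment:** "Once the patient is randomized, the CCRC intern will notify the ED pharmacist who will determine if patient is currently taking basal insulin". This comes after allocation and has no arm restriction.
- **Intervention group-specific:** "If the patient is in the intervention group, the ED pharmacist and/or research intern will determine if the patient was taking basal insulin". This is conditional on being in that arm.
- **Variable list:** prior basal use and home insulin dose each have the role "Treatment determination if in intervention arm". Neither is marked as descriptive or as a covariate.

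The Randomization section uses one list without strata: a staff member "will assign either the number 1 (control) or 2 (intervention) to each row number, ensuring 75 of each are populated". The row is uncovered at enrollment, and no masking of treatment is described afterwards.

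The Statistical analysis plan compares the primary outcome by a two-sided t-test, or: "If the distribution is non-parametric, that outcome will be analyzed using a Wilcoxon rank sum test". It expects length of stay to fall in the second case. The only adjustment it foresees is for differences in the timing of outcome labs. It names no baseline covariate, stratum or subgroup.

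**The concern.** The factor that splits the intervention into two regimens is a baseline trait that could also be related to length of stay. Three things follow from the way it is handled.

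1. Neither the allocation nor the analysis protects against a chance difference between arms in the share of prior users.
2. The variance that this factor and presenting severity could explain stays in the error term, although both are already on the data form.
3. The Summary and the Background both say that no prospective trial has examined early resumption of home basal insulin. The planned result pools resuming with starting. An estimate for either regimen needs controls classified in the same way. In the intervention arm a dose depends on the answer and a pharmacist verifies it. In the control arm nothing depends on it, and the arm is known when the question is asked. The value may therefore be less carefully obtained in controls, and two of the three sections do not clearly require it there.

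**Working it through.** **Inputs (Sample size section):** 66 per arm, alpha 0.05, coefficient of variation (CV) 0.6, 80% power, ratio about 1.31. The Statistical analysis plan makes the test two-sided. The documents give neither the share of prior basal users nor the variance that any covariate explains, so both are assumptions shown as ranges.

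**1. The plan's own figure.** The log-scale SD is √ln(1 + 0.6²) = √ln 1.36 = 0.5545. The effect is ln 1.31 = 0.270. The standard error is 0.5545 × √(2/66) = 0.0965, and 0.270/0.0965 = 2.797. Normal power is Φ(2.797 − 1.960) = 0.799. The noncentral t gives 0.793, and exactly 80% is reached at a ratio of 1.313. The stated figure reproduces, so there is no arithmetic error here.

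**2. Adjustment.** Replace the SD by 0.5545 × √(1 − R²), where R² is the share of log-stay variance explained jointly by the covariates (noncentral t, 66 per arm):

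| Assumed joint R² | Residual SD | Power at 1.31 | Ratio detectable with 80% power |
|---|---|---|---|
| 0 | 0.555 | 79.3% | 1.313 |
| 0.05 | 0.540 | 81.3% | 1.304 |
| 0.10 | 0.526 | 83.3% | 1.295 |
| 0.20 | 0.496 | 87.4% | 1.276 |

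**3. How much could prior basal use explain alone?** For a binary factor with share p and log-scale gap d, R² = p(1 − p)d²/0.5545². For R² = 0.10, d = 0.351 at p = 0.5, which means stays differing by a ratio of 1.42 between users and non-users. At p = 0.8, d = 0.438 and the ratio is 1.55. For R² = 0.20 the ratios are 1.64 and 1.86. The documents offer nothing to support gaps of that size, so the gain in step 2 cannot be credited to this factor by itself.

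**4. Chance imbalance and power by stratum.** The imbalance column takes two independent binomial samples of 66. The power columns take equal numbers per arm within each stratum and the same CV.

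| Assumed share of users | Chance of a gap of at least 10 points between arms | Users / non-users per arm | Power at 1.31, users | Power at 1.31, non-users |
|---|---|---|---|---|
| 50% | 26% | 33 / 33 | 50% | 50% |
| 60% | 25% | 40 / 26 | 58% | 41% |
| 70% | 22% | 46 / 20 | 64% | 32% |
| 80% | 16% | 53 / 13 | 70% | 22% |
| 90% | 6% | 59 / 7 | 75% | 13% |

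A 10-point gap moves the log ratio by 0.10 × d. Even with d = 0.351 that is 0.035, or 13% of the 0.270 the trial is sized to detect. This is worth removing but would not decide the result.

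An interaction test would need a ratio of ratios of 1.72 (50% users) to 2.41 (90% users) for 80% power.

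**The case against.** **The test is valid as it stands.** Prior basal use is fixed before randomization and does not enter the primary test, so late ascertainment cannot bias that test, and its type I error already allows for chance imbalance. This stands in full. A reader might infer that the primary comparison is biased; the documents do not support that.

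**Controls may well have the value.** Enrollment words the step for any randomized patient. The conditional sentence sits under a heading about the intervention arm and does not say that controls are not asked. Where the form restricts a field to one arm it says so, as with one hypoglycemia field marked for controls only; these two fields carry no such mark. So it would be wrong to conclude that the value will be missing in controls. What remains is that the sections disagree and that nothing requires equal ascertainment.

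**The pooled strategy is the declared objective.** The Summary names both regimens as one policy, and no aim asks for effects by regimen. This also stands. The lack of a regimen-specific test is not a failure against the stated aims, and step 4 shows that the trial could not support one. A descriptive estimate is still useful given the rationale, provided it is labelled as such.

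**The gain is assumed.** No R² is given in the documents, nor any link between prior basal use and stay. Not taking basal insulin need not mean newly diagnosed diabetes. The CV comes from a length of stay that is not stated to be ICU stay, the primary outcome. These limits apply to every figure in step 2.

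**Conclusion.** The concern holds as a matter of efficiency and interpretability, not validity. Under an assumed joint R² of 5–20% and the plan's CV of 0.6 carried over to ICU stay, adjustment would raise power at a ratio of 1.31 by about 2 to 8 percentage points. The low end of that range is a small gain. It belongs to the covariates together. Separate conclusions on the two regimens are out of reach at 132 patients, whatever is done about ascertainment. The change is still worth making, because the covariates are already on the form, and comparable classification of controls is hard to restore once enrollment has run with the arm known.

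**What to change.** 1. Record prior basal use and home dose for every patient on the REDCap screening checklist, before the allocation row is uncovered. Pump and combination-insulin use are exclusions checked there, so home insulin is already partly reviewed at that point.
2. Reconcile Enrollment, the intervention section and the variable list so that all three say this. Give both fields a role in both arms.
3. Prespecify the primary ICU-stay analysis as a linear model on log stay, adjusted for prior basal use and presenting pH or bicarbonate. The power calculation already works on the log scale. A Wilcoxon test stratified by prior basal use is an alternative, with a smaller gain because it uses one factor only.
4. Report the treatment effect with a confidence interval in prior users and in non-users, labelled descriptive, with no claim resting on either.

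The cost is one question moved to screening and a few sentences in the protocol and analysis plan. If the intervention section has been followed literally, home insulin must also be checked in about 66 controls. Sample size, allocation list and treatment rules are unchanged.
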